11.8.8.2 Pregnancy

Subjects will be counseled to inform the investigator of any pregnancy that occurs during study treatment and within 90 days after the last dose of the study drug.

If a female subject or the female partner of a male subject becomes pregnant while participating in the study, study drug must be permanently discontinued immediately. For male subjects, study drug does not need to be permanently discontinued if the female partner's pregnancy resulted from donated sperm or sperm banked before study drug exposure ([Section 11.8.8.1](#)). The investigator must notify the medical monitor and Vertex GPS within 24 hours of the site's knowledge of the subject's (or partner's) pregnancy using the Pregnancy Information Collection Form.

If the subject is confirmed to be on study drug, the subject or partner will be followed until the end of the pregnancy and the infant will be followed for 1 year after the birth, provided informed consent/assent is obtained. A separate ICF will be provided to explain these follow-up activities. Pregnancy itself does not constitute an AE.

12 STATISTICAL AND ANALYTICAL PLANS

This section presents a summary of the planned analyses for the Treatment Cohort in this protocol. Statistical analysis details for the Treatment Cohort will be provided in the Statistical Analysis Plan (SAP) will be finalized before the clinical data lock for the study.

No analysis will be performed for the Observational Cohort.

12.1 Sample Size and Power

Study VX14-661-110 is a rollover study that plans to enroll subjects from Studies VX13-661-103, VX14-661-106, VX14-661-108, VX14-661-109, VX14-661-111, and other eligible Vertex studies investigating VX-661 in combination with ivacaftor who meet the eligibility criteria for this study. Approximately up to 1375 subjects are potentially eligible to be enrolled from the following parent studies: 40 subjects from Study VX13-661-103, 490 subjects from Study VX14-661-106, up to 300 subjects from Study VX14-661-108, up to 200 subjects from Study VX14-661-109, and 45 subjects from Study VX14-661-111, if eligible.

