- Pharmacokinetic (PK) parameters of VX-661, a VX-661 metabolite (M1-661), ivacaftor, and an ivacaftor metabolite (M1-ivacaftor)

Observational Cohort

- Safety, as determined by related serious adverse events (SAEs)

Number of Subjects Study VX14-661-110 is a rollover study that plans to enroll subjects from Studies VX13-661-103, VX14-661-106, VX14-661-107, VX14-661-108, VX14-661-109, VX14-661-111, and other eligible Vertex studies investigating VX-661 in combination with ivacaftor who meet the eligibility criteria for this study. Approximately up to 1375 subjects are potentially eligible to be enrolled from the following parent studies: 40 subjects from Study VX13-661-103, 490 subjects from Study VX14-661-106, 300 subjects from Study VX14-661-107, up to 300 subjects from Study VX14-661-108, up to 200 subjects from Study VX14-661-109, and 45 subjects from Study VX14-661-111.

Study Population Treatment Cohort

Male and female subjects 12 years of age and older with CF who are homozygous or heterozygous for the *F508del-CFTR* mutation

Observational Cohort

Male and female subjects <18 years of age (age on the date of informed consent/assent in the parent study) with CF who are homozygous or heterozygous for the *F508del-CFTR* mutation

Investigational Drug **Treatment Cohort**

Active substance: VX-661 and ivacaftor

Activity: CFTR corrector and potentiator (increased chloride ion [Cl⁻] secretion)

Strength and Route of Administration: VX-661 100 mg/ivacaftor 150-mg fixed-dose combination (FDC) film-coated tablet for oral administration

Active substance: ivacaftor

Activity: CFTR potentiator (increased Cl⁻ secretion)

Strength and Route of Administration: ivacaftor 150-mg film-coated tablet for oral administration

Study Duration Treatment Cohort

Study drug will be administered for approximately 96 weeks [with a Safety Follow-up Visit 28 days (\pm 7 days) after the last dose.

Observational Cohort

For the Observational Cohort, maximum subject participation will be approximately 2 years.

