6.2 Sample Size and Power

Part A

Treatment Cohort

1,044 eligible subjects are enrolled from the following parent studies:

- 23 subjects from Study 103.
- 464 subjects from Study 106.
- 159 subjects from Study 107.

- 227 subjects from Study 108.
- 138 subjects from Study 109.
- 33 subjects from Study 111.

Observational Cohort

No patient enrolled in observational cohort.

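### Does the mismatch between the stated 1375 subjects and a parent-study list that sums to 1075 in Protocol 12.1 call for a change to the plan?

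*Protocol*

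**What the plan says.** Protocol Section 12.1, the sample-size section, opens by naming the studies that will feed the rollover: 103, 106, 108, 109, 111 and other eligible studies of the combination. Study 107 is not named. The section then states "Approximately up to 1375 subjects are potentially eligible to be enrolled from the following parent studies" and gives a count for each: 40 for Study 103, 490 for 106, at most 300 for 108, at most 200 for 109 and 45 for 111. It contains nothing else: no alpha, power, effect size or precision target.

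The synopsis (Number of Subjects) makes the same statement with the same total, but its list of feeder studies includes Study 107, and its counts include "300 subjects from Study VX14-661-107, up to 300 subjects from Study VX14-661-108".

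Elsewhere Study 107 is treated as a parent study throughout. Protocol Sections 8.1 and 8.2.1 name it among the parent studies, and Section 9.1 names it in the eligibility criteria. Section 8.2.1 also reports that it was stopped early for futility. SAP Section 6.2 reports 1,044 subjects enrolled, of whom "159 subjects from Study 107". SAP Section 9.7.1 includes it among the parent studies whose adverse-event tables go into the clinical study report.

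**The concern.** The list and the total stand in the same sentence and disagree by 300, in the only part of the protocol's statistical section that gives a number of subjects. On its face, the planned size is either too large for the studies listed or the list is incomplete.

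The omission could also be read as deliberate. Study 107 was stopped for futility, and it is missing from Section 12.1 twice, once from the named studies and once from the counts. A reader might conclude that its subjects were meant to be outside the planned population, while the synopsis and the eligibility section say they are inside it. Because safety is the primary objective and is pooled over all dosed subjects, whether a parent study of this size belongs would matter for the primary analysis if Section 12.1 settled the question. A smaller planned number would also mean less ability to rule out rare adverse events.

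**Working it through.** **Step 1: the plan's own total, from the list in Section 12.1.**

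40 (103) + 490 (106) + 300 (108) + 200 (109) + 45 (111) = 1075.

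The stated total is 1375, and 1375 − 1075 = 300. The total does not reproduce.

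**Step 2: the same total, from the synopsis list.**

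40 (103) + 490 (106) + 300 (107) + 300 (108) + 200 (109) + 45 (111) = 1375.

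The total reproduces exactly. The five shared counts are identical in the two places, and the shortfall in Section 12.1 equals the synopsis count for Study 107.

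**Step 3: other explanations.**

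- Rounding does not explain the gap. The counts for 108 and 109 are already maxima, and the sum is still 300 short.
- The allowance for other eligible studies does not explain it. The 1375 is tied to the studies that follow it, and the synopsis reaches 1375 without any additional study.

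Neither document states the cause. Loss of Study 107 from the list, with the total left as it was, is the explanation that fits every number.

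**Step 4: actual enrolment, from SAP Section 6.2.**

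23 (103) + 464 (106) + 159 (107) + 227 (108) + 138 (109) + 33 (111) = 1044.

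This agrees with the SAP's stated total. Without Study 107 it would be 1044 − 159 = 885. Study 107 contributes 159/1044 = 15.2% of those enrolled, so it was plainly treated as a source of subjects.

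**Step 5: does anything depend on the list in Section 12.1?**

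- *Eligibility* is set by Protocol Section 9.1, which names Study 107.
- *The Safety Set* in Protocol Section 12.2 and SAP Section 7.3 is everyone who received at least one dose in this study. The SAP adds that genotype is irrelevant. Neither definition refers to the parent study.
- *The main efficacy sets* in SAP Section 7.1 are defined by rollover from Studies 106 and 108, so Study 107 is not involved. The same section records that subjects from 107 and 109 rolled over and were later discontinued.
- *Power or precision:* none is stated. Protocol Section 12.3.5 makes the safety analysis descriptive, and SAP Section 9.6.2 excludes hypothesis tests between groups.

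**Step 6: size, on the least favourable reading.** Suppose one wants the exact one-sided 95% upper bound on the incidence of an adverse event that is never observed, 1 − 0.05^(1/n). This criterion is an illustration and appears in neither document.

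| n | Source | Upper bound |
|---|---|---|
| 1375 | stated ceiling | 0.218% |
| 1075 | Section 12.1 list | 0.278% |
| 1044 | SAP, enrolled | 0.287% |

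The two planning figures differ by 0.06 percentage points. The bound that would apply to the data is the one at 1044, and it is the same whichever way Section 12.1 reads.

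**The case for a change.** The strongest case for acting is that this is a plain arithmetic contradiction in current protocol text, in the one section devoted to sample size. It is not a damaged table, and it is not a difference from an amendment log. Study 107 is absent from both the named studies and the counts, and because it was stopped for futility the omission could pass for intent. Its subjects make up 15.2% of those enrolled and are in the primary safety analysis, so the statistical section ought to name their source.

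The arithmetic stands in full. The claim that the population is left ambiguous does not. Section 12.1 counts expected sources; it neither sets eligibility nor defines an analysis set, and the sections that do leave no doubt about Study 107. Describing the total as 300 too high (300/1075 = 28%) also does not hold up. If Study 107 fell out of the list, then the list is short and 1375 is the intended ceiling. Restating the total as 1075 would conflict with the synopsis, with Sections 8.1 and 9.1, and with the 159 subjects already enrolled.

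**Conclusion.** The mismatch is real and amounts to exactly 300 subjects, but it is a clerical slip and no change to the plan follows. The stated 1375 is correct as a ceiling, and what is missing is one study from an enumeration. Putting it back would leave the total, eligibility, analysis sets, denominators and results as they are. A reader can recover the full breakdown from the synopsis, and analysts will work from the SAP's 1,044, which sums correctly. Under Protocol Section 13.2.3 a protocol modification needs investigator and sponsor approval and goes to the regulators, so a separate amendment for this line would bring process and no statistical gain.

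This conclusion rests on two readings. The first is that Study 107 was dropped by oversight. That is an inference, but the exact gap of 300, the five matching counts, the eligibility text and the actual enrolment all support it. The second is that the ceiling serves no inferential purpose, which follows from the absence of any power or precision statement in either document.

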12.2 Analysis Sets

For subjects in the Treatment Cohort, the assignment to analysis sets will be done before the clinical data lock for the study.

The All Subjects Set is defined as all subjects who signed informed consent (enrolled) and have received at least 1 dose of study drug in Study VX14-661-110. This analysis set will be used in subject listings and disposition summary tables unless otherwise specified.

The Full Analysis Set (FAS) is defined as all enrolled subjects who have received at least 1 dose of study drug in Study VX14-661-110 and have one of the following mutations: *F508del/F508del*, *F508del/Residual function*, and *F508del/Gating*. The FAS is to be used in the efficacy analyses unless otherwise specified.

The Safety Set is defined as all subjects who received at least 1 dose of study drug in Study VX14-661-110. The Safety Set is to be used for the safety analyses unless otherwise specified.

12.3 Statistical Analysis

12.3.1 General Considerations

Continuous variables will be summarized using the following descriptive summary statistics: the number of subjects (n), mean, SD, median, minimum value (min), and maximum value (max).

Categorical variables will be summarized using counts and percentages.

Baseline value, unless otherwise specified, for efficacy and safety analyses, will be defined as the most recent non-missing measurement (scheduled or unscheduled) collected before the first dose of VX-661/ivacaftor or ivacaftor alone (in the parent study or Study VX14-661-110, but

after the washout period, if applicable). For subjects who received VX-661 and ivacaftor combination therapy in the parent study, the baseline will be the same as the baseline in the parent study. For subjects who received placebo or ivacaftor in the parent study and transitioned to VX-661/ivacaftor in Study VX14-661-110, the baseline will be the baseline in Study VX14-661-110. For subjects from Study VX14-661-108, the parent study baseline will be the baseline for Treatment Period 2 in Study VX14-661-108. For subjects from Study VX13-661-103, the parent study baseline will be the baseline in the Open-label Phase of Study VX13-661-103 for subjects who participated in the Open-label Phase or the baseline in Study VX14-661-110 for subjects who did not participate in the Open-label Phase of Study VX13-661-103.

Change (absolute change) from baseline will be calculated as postbaseline value - baseline value.

Relative change from baseline will be calculated as (postbaseline value - baseline value)/baseline value.

Efficacy Analysis Period will include the time from the first dose of VX-661/ivacaftor or ivacaftor alone (in the parent study or Study VX14-661-110, but after the washout period, if applicable) to the last scheduled efficacy visit in Part of Study VX14-661-110. For subjects who participate in another qualified Vertex study before completing Study VX14-661-110 assessments and re-enroll in Study VX14-661-110, the Efficacy Analysis Period will exclude the time between the last dose before the discontinuation from Study VX14-661-110 and the first dose after re-enrollment in Study VX14-661-110.

Treatment-emergent (TE) Period will include the time from the first active dose of VX-661/ivacaftor or ivacaftor alone (in the parent study or Study VX14-661-110, but after the washout period, if applicable) to the Safety Follow-up Visit or 28 days after the last dose of the study drug for subjects who do not have a Safety Follow-up Visit or who have their Safety Follow-up Visit more than 35 days after the last dose of Study VX14-661-110. For subjects who participate in another qualified Vertex study before completing Study VX14-661-110 (96 weeks) and re-enroll in Study VX14-661-110, the TE Period will exclude the time spent in the other study. Specifically, the TE Period will be interrupted 28 days after the last dose of study drug in Study VX14-661-110 and will restart with re-enrollment into Study VX14-661-110 when the subject takes the first dose of study drug.

Note, in the Efficacy Analysis and TE Periods, for subjects who received the active study drugs in Study VX14-661-108, the first active dose will be the first dose of VX-661/ivacaftor or ivacaftor monotherapy in the Treatment Period 2 of Study VX14-661-108. For subjects who received the active study drug from Study VX13-661-103, the first active dose will be the first active dose of study drug in the Open-label Phase of Study VX13-661-103.

12.3.2 Overview of Analysis Strategies

- Study VX14-661-110 data will not be analyzed in isolation as patients received different durations of treatment in the parent studies. Study VX14-661-110 data will be integrated with the parent study data for each subject from the first active dose of VX-661/ivacaftor or ivacaftor alone (after the washout period, if applicable).
- The analysis baseline will be the last non-missing measurement prior to the first active dose of VX-661/ivacaftor or ivacaftor alone [in the parent study (after the washout period, if

applicable) or Study VX14-661-110]. All post-baseline measurements will be mapped to the uniform analysis visit windows based on the study days counted from the first active dose of VX-661/ivacaftor or ivacaftor alone (after the washout period in the parent study, if applicable) to make the results more comparable and interpretable.

- For subjects in Study VX14-661-110, the safety analyses will be performed on all of the subjects pooled together. The efficacy analysis will be performed on each CFTR mutation group separately (*F508del/F508del*, *F508del/Residual Function*, and *F508del/Gating*).

12.3.3 Background Characteristics

Subject disposition, demographic and baseline characteristics, prior and concomitant medications, study drug exposure and compliance, and other background characteristics will be summarized. Additionally, all subject data will be presented in subject data listings.

12.3.3.1 Subject Disposition

All summaries in this section will be performed on all subjects pooled together based on the Safety Set, and performed on each CFTR mutation group separately (*F508del/F508del*, *F508del/Residual Function*, and *F508del/Gating*) based on the FAS, unless otherwise specified in the SAP. No statistical hypothesis testing will be performed.

Subject disposition analysis will be performed. The number and percentage of subjects in the following categories will be summarized as appropriate:

- All Subjects Set
- Safety Set
- FAS
- Completed study drug treatment
- Prematurely discontinued treatment and the reasons for discontinuation
- Prematurely discontinued the study during the Safety Follow-up and the reasons for discontinuations

12.3.3.2 Demographics and Baseline Characteristics

All summaries in this section will be performed on all subjects pooled together based on the Safety Set, and performed on each CFTR mutation group separately (*F508del/F508del*, *F508del/Residual Function*, and *F508del/Gating*) based on the FAS, unless otherwise specified in the SAP. No statistical hypothesis testing will be performed. Demographics and baseline characteristics of Study VX14-661-110 will be based on the demographics and baseline characteristics in the parent studies.

Demographic, background (e.g., medical history), and baseline characteristics will be summarized. Baseline characteristics will be based on the parent study baseline characteristics. Protocol deviations/violations will be provided as a subject data listing only. Important protocol deviations/violations will be listed or summarized.

The following demographics and baseline characteristics will be summarized for the FAS: sex, race, ethnicity, age, weight, height, BMI, region, baseline ppFEV₁, and baseline score of CFQ-R respiratory domain.

12.3.3.3 Prior and Concomitant Medications

All summaries in this section will be performed on all subjects pooled together based on the Safety Set, unless otherwise specified in the SAP. No statistical hypothesis testing will be performed.

Medications used in this study will be coded by using the World Health Organization-Drug Dictionary Enhanced and categorized as the following:

- **Prior medication:** any medication that started before the first active dose of study drug (in the parent study or in Study VX14-661-110, after the washout period, if applicable), regardless of when it ended. In addition, for subjects who participate in another qualified Vertex study before completing Study VX14-661-110 assessments and re-enroll in Study VX14-661-110, any medication that was collected with a start date after the informed consent/assent for re-enrollment is signed and before the first dose of VX-661/ivacaftor after re-enrollment in Study VX14-661-110 will also be considered as prior medication, regardless of when medication was discontinued.
- **Concomitant medication:** medication continued or newly received at, or after, initial dosing of study drug through the end of the TE Period.
- **Post-treatment medication:** medication continued or newly received beyond the TE Period.

A given medication can be classified as a prior medication, a concomitant medication, or a post-treatment medication; both prior and concomitant; both concomitant and post-treatment; or prior, concomitant, and post-treatment. If a medication has a missing or partial missing start/end date or time and it cannot be determined whether it was taken before initial dosing, concomitantly, or beyond the TE Period, it will be considered as prior, concomitant, and post-treatment.

Concomitant medications will be summarized descriptively for the Safety Set by: 1) preferred name; and 2) anatomic class (ATC) level 1, ATC level 2, and preferred name.

The medications (prior, concomitant, post-treatment) will be listed.

12.3.3.4 Study Drug Exposure and Compliance

All summaries in this section will be performed on all subjects pooled together based on the Safety Set, and performed on each CFTR mutation group separately (*F508del/F508del*, *F508del/Residual Function*, and *F508del/Gating*) based on the FAS, unless otherwise specified in the SAP. No statistical hypothesis testing will be performed.

Treatment Cohort

Exposure to study drug (i.e., duration of treatment) will be summarized for the FAS in terms of duration of treatment a subject received (in days), defined as the last day minus the first day of dosing with VX-661/ivacaftor or ivacaftor monotherapy in the parent study (but after the washout period, if applicable) or VX-661/ivacaftor in Study VX14-661-110, plus 1.

Dosing compliance will be summarized for the FAS and is calculated as the actual number of days at which study drug was administered, as a percentage of the duration of study drug exposure.

Duration of treatment and dosing compliance will be summarized by descriptive summary statistics.

12.3.4 Efficacy Analysis

Treatment Cohort

Assessment of the long-term efficacy and tolerability of VX-661 /ivacaftor for subjects in the Treatment Cohort is a secondary or other objective of this study. The efficacy analysis will be performed on each CFTR mutation group separately (*F508del/F508del*, *F508del/Residual function*, and *F508del/Gating*). All data collected during the efficacy analysis period through the end of Study VX14-661-110 will be summarized.

12.3.4.1 Analysis of Primary Efficacy Variables

Not applicable since efficacy is not a primary objective.

12.3.4.2 Analysis of Secondary [REDACTED] Efficacy Variables (Treatment Cohort)

- **Absolute change from baseline in ppFEV₁**

One of the secondary efficacy endpoints is the absolute change from baseline in ppFEV₁. The primary analysis for this secondary endpoint will be based on a mixed-effect repeated-measure model (MMRM), as applicable. The model will include the absolute change from baseline in ppFEV₁ as the dependent variable; treatment group, visit, and treatment-by-visit interaction as fixed effects; and subject as a random effect with or without adjustment for sex, age, baseline ppFEV₁.

In the model, visit will be treated as a class variable, assuming an unstructured covariance matrix to model the within-subject variability. This model imposes no assumptions on the correlational structure and is considered robust. Denominator degrees of freedom for the F test for fixed effects will be estimated using the Kenward-Roger approximation. If there is a convergence problem due to the use of an unstructured covariance matrix, a compound symmetry covariance structure will be used to model the within-subject errors. With a mixed-effects model based on a restricted maximum likelihood estimation used for the primary analysis and assuming that, conditional on fixed and random effects, data are missing at random, no imputation of missing data will be performed.

Descriptive summary statistics including number of subjects, mean, standard error, and least square mean (LS mean), along with the associated 95% CI will be provided for each visit.

- **Relative change from baseline in ppFEV₁**

Analysis of this variable will be performed using the same MMRM model as described for the absolute change from baseline in ppFEV₁.

- **Number of pulmonary exacerbations**

The number of pulmonary exacerbations will be analyzed using a negative binomial regression model as applicable. The independent variables will include visit, sex, age, baseline ppFEV₁. The event rate and 95% CI will be reported.

- **Absolute change from baseline in body mass index (BMI)**

Analysis of this variable will be similar to the model as described for the absolute change in ppFEV₁ from baseline, with the addition of baseline BMI as the covariate.

- **Absolute change from baseline in BMI z-score**

Analysis of this variable will be similar to the model as described for the absolute change in ppFEV₁ from baseline, with the addition of the BMI z-score at baseline as a covariate for subjects <20 years old at the time of the Screening Visit in the parent study.

- **Absolute change from baseline in CFQ-R respiratory domain score**

Analysis of this domain will be similar to the model as described for the absolute change in ppFEV₁ from baseline, with the addition of the CFQ-R respiratory domain score at baseline as the covariate.

- **Absolute change from baseline in body weight**

Analysis for this variable will be similar to the model as described for the absolute change in ppFEV₁ from baseline, with the addition of the body weight at baseline as a covariate.

- **Absolute change from baseline in body weight z-score for subjects aged <20 years at screening in the parent study**

[figure not shown]
Analysis of this variable will be similar to the model as described for the absolute change in ppFEV₁ from baseline, with the addition of the body weight z-score at baseline as a covariate for subjects <20 years old at the time of the Screening Visit in the parent study.

- **Absolute change from baseline in height z-score for subjects aged <20 years at screening in the parent study**

Analysis of this variable will be similar to the model as described for the absolute change in ppFEV₁ from baseline, with the addition of the height z-score at baseline as a covariate for subjects <20 years old at the time of the Screening Visit in the parent study.

[figure not shown]
- **Time-to-first pulmonary exacerbation**

Time-to-first pulmonary exacerbation is defined as days starting from the first dose of VX-661 and ivacaftor combination therapy to the first event of pulmonary exacerbation. A subject without exacerbation before the end of the Efficacy Analysis Period of Study VX14-661-110 will be considered censored at the end of the Efficacy Analysis Period. Kaplan-Meier method will be used to produce graphical presentation of the survival distribution (exacerbation-free survival) and to estimate cumulative survival rates by the CFTR mutation groups.

- **Absolute change in Brody/CF-CT scores from baseline using LDCT scans for subjects enrolling from Study VX15-661-112**

Only applicable for the subjects enrolling from Study VX15-661-112. The absolute values and changes from baseline of the Total Brody/CF-CT scores  will be summarized descriptively.

